4. ANTICIPATED RISKS

One potential risk to participants in this study is a loss of confidentiality. To mitigate this risk, all research staff, including peer parents, will be trained in the protection of human subjects and will be instructed in maintaining strict confidentiality. In order to de-identify data, we will assign each participant a random identification number. Only these numbers will be associated with the assessment materials. One

master document that links participant names and numbers will be retained in a password protected computer file accessible only to authorized study staff. Participants will be assured that the decision to take part in the study will not affect access to programming or resources. While participation in the program involves completing the intervention at Odyssey House, receiving postcard reminders, and touching base with peer interventionists regularly over two weeks (thus making it possible for other individuals to observe participants being administered the intervention or receiving study-related communications), we believe this risk is minimal. However, we will also attempt to conceal participation status in a number of ways. Peer parents will be trained to take reasonable precautions to prevent revealing parents' participation in the program, including closing the door to the intervention room and not referring to participants' status in the intervention outside of this private space.

We expect any discomfort participants may feel while completing assessment questionnaires (i.e., frustration, boredom, and fatigue) to be short-lived. However, in the event that participants are either disturbed or concerned about reactions to the questionnaires, we will encourage them to discuss these concerns with the research staff. They will be put in touch with mental health staff at Odyssey House, and/or the PI ([name]), a licensed clinical psychologist, if concerns are not satisfactorily addressed. We will also discuss with all participants the nature of the Certificate of Confidentiality during the assent and consent procedures. If participants report feeling uncomfortable answering certain questions, they will be reminded that they are allowed to skip items and still be compensated for participation. Based on previous experiences collecting data from low-income adults, we anticipate very low levels of non-response.

In the event that a participant discloses suicidal ideation or intent, involvement in psychical abuse/neglect, and/or urgent physical and mental health concerns arise for the parent or child, the RA or interventionist will confer with [name] and the medical and mental health providers on staff at Odyssey House to determine next steps. [name], in collaboration with medical and mental health providers at Odyssey House will determine the appropriate course of action. In extreme circumstances, this may involve contacting authorities. The PI ([name]) and Co-I [name] have conducted similar clinical trials and [name] has also used similar methods and interventions with Flint, MI-based samples and, from this experience, believe the possibility of having to report participants to authorities is extremely rare. Given that we are not specifically asking about suicidality, we also expect any spontaneous disclosure of suicidality by the participant to be extremely rare. Nevertheless, any participant disclosure of harm to self or others will be treated seriously and the PI will immediately and directly contact Odyssey house medical and mental health providers to follow-up with the participant to clarify their report of harm to self/others and gather more information.

In the rare event that such disclosures are determined to be required by law, we will report only information directly provided by the participant related to child maltreatment (defined as physical or mental injury, sexual abuse, neglect, or other circumstance whether the welfare of the child is threatened). Prior to participation, participants will be given clear verbal and written details (during consent procedures) around these requirements and informed of the research team's ethical and legal obligations to protect the safety of vulnerable individuals. Participants will also be given multiple opportunities to ask questions regarding both reporting requirements and the reporting process and encouraged to reach out to the PI (a licensed clinical psychologist) to address any concerns that they may have. Participants who are reported to authorities under these circumstances will be allowed to remain in the study, but their data will not be used and a replacement participant will be recruited. The research team has already fully discussed these reporting requirements and received support for these procedures from agency leadership at both recruitment sites. Researchers have worked extensively with Odyssey House staff on the development of research procedures, including addressing any concerns the provider may have that may arise during the completion of this project.

Stakeholders

The only foreseeable risk to stakeholders is discomfort at answering some of the questions. We do not anticipate this to be frequent and stakeholders are able to skip any questions they don't want to answer.

5. ANTICIPATED BENEFITS

The primary anticipated benefit of this research to parents and society is the possible improvement in parent-child relationship quality and related constructs.

6. RENUMERATION/COMPENSATION

Parent participants will be offered payment for taking part in each assessment (including written assessments, parent-child observation sessions and key informant interviews), as well as completing daily practice of the intervention over two weeks. Incentives will be provided on ClinCards.

Weeks from Enrollment	1	2	3	4	5-6
Activity	Assessment 1 (observation and assessment)	Intervention + MCQ and Parenting Joy survey	Daily postcard reminders and regular (3-7) check-ins with peers	Assessment 2 (observation and assessment)	Interview
Incentives	\$15		\$14	\$15	\$15

Stakeholders will receive a one-time payment for completion of the key informant interview. Incentives for stakeholders will be provided on ClinCards.

7. COSTS

There are no costs to the participant to take part in this study.

8. ALTERNATIVES

The alternative to participants is not participating in this research.

9. CONSENT PROCESS AND DOCUMENTATION

Research assistants (peer parent) will meet with eligible parent participants in small, private rooms at Odyssey House to review the consent form and answer any questions that participants may have. If a participant appears to be under duress or undue influence or does not have sufficient time to complete the consent procedures, a follow-up meeting will be scheduled. As part of the consent process, the RA will explain the study, its duration, risks and requirements and allow the participant to ask any questions they may have. Participants will be informed that they will be identified only by a randomly assigned number and that only one log linking their ID and names will be kept in a password protected computer file stored on a secure HITECH-compliant server and accessible only to a small number of authorized members of the research team. They will also be informed that the intervention session, parent-child interaction, and the key informant interview will be recorded for research purposes and that these recordings and all evaluation materials and the log linking participant ID and names will be stored securely, only accessible to the study team, and destroyed three years after completion of the intervention. The participant will be provided a copy of the signed consent.

All consent documents will be stored in a locked file cabinet in a secure location at Odyssey House or Henry Ford Health System and kept apart from any other study data.

All children over the age 7 and older participating in the observation session will be assented before the observation with their parent begins. Prior to taking part in the observational assessment, a research assistant will explain their participation in the study (over phone or web conferencing) and allow for time for the child to ask questions. Verbal assent will be documented in REDCap.

Stakeholder Consent – Key Informant Interviews:

For stakeholder interviews, we are requesting a waiver of written consent. The interview poses no more than minimal risk, and a written consent form would be the only record linking the stakeholder participant to the study – we are otherwise not collecting any identifiable data as part of the interviews. The stakeholders are not receiving an intervention and involve no procedures for which written consent is normally required outside of the research context. Consent information will be reviewed with all stakeholders prior to beginning the interview, and we will provide stakeholders with a copy of the consent information sheet to review and keep.

10. WITHDRAWAL OF SUBJECTS

There are no anticipated circumstances under which participants will be withdrawn from the research without their consent. This includes participants that leave Odyssey House – they will not be withdrawn and can continue in the study if they are interested in doing so. Participants who decide to withdraw will not face any penalty or denial of services.

11. PRIVACY AND CONFIDENTIALITY

All participants will be assigned a random study ID. Only one log linking participants names and their IDs will exist and it will be kept separate from all other study materials (including consent forms and assessment packets/recordings). All study materials will be kept in encrypted data files on a password protected computer. Consent forms will be kept separately from study data and will be housed in locked areas in secured offices at Henry Ford or Odyssey House and accessible only by the study team. For stakeholder participants, no identifiable information will be collected. Study materials will be collected by research team members and will only be used by members of the research team. All study materials will be destroyed three years after the completion of the study, consistent with recommended guidelines.

All video and audio recordings will be saved with study ID only on a secure folder on secure servers at HFHS or Odyssey House. Only study personnel will have access to this folder and the video recordings. Audio files will be uploaded to a secure AI-based transcription platform for transcription purposes. Transcripts will be reviewed by the study team and any PHI will be removed before saving the file to a secure study folder accessible only to the research team. Audio files and transcripts will be saved with a study ID only. Once transcribed, audio files will be deleted as soon as possible.

In addition, a Certificate of Confidentiality (CoC) is automatically given to all NIH-funded studies to protect the privacy of research subjects by prohibiting disclosure of identifiable, sensitive research information to anyone not connected to the research except when the subject consents, or when required by law for reporting medical emergencies, serious threats of harm to self or others, child abuse or neglect, or elder abuse.

Important HIPAA Concerns

No medical records are being used for this study.

12. DATA ANALYTIC AND SAFETY MONITORING PLAN

[name] will be responsible for overseeing the implementation and execution of the data and safety monitoring plan. All research staff (including peer parents) will complete relevant human subjects protection training. [name] will also ensure that all participants in the study meet specified inclusion/exclusion criteria by reviewing enrollment with research staff at regular study team meetings. Data will be monitored on an ongoing basis and reviewed by the PI at regular intervals to identify any problems or concerns. Analyses will be conducted only after all data is collected, deidentified, and cleaned, thus limiting the possibility of deidentification.

Any findings shared with community stakeholders will be done in aggregate and reflecting mean-level trends. Data will be safeguarded against breaches of confidentiality using the procedures outlined above. These processes include removing identifiable information from data and coding assessment forms with ID numbers only. All data will be kept securely in locked file cabinets accessible only to research staff. Community partners and peer parents will not have access to any assessment materials. Any computers containing electronic data files will be password-protected, stored in locked cabinets in locked offices, and accessible only by study personnel. Only the research staff will have access to the data. The Certificate of Confidentiality from NIH which will protect against requests to disclose sensitive research information, within the bounds of the law.

Adverse Events (AEs) and Serious Adverse Events (SAEs), as defined by the DHHP Office of Human Research Protections, will be monitored by the PI ([name]). Any AEs will be recorded by research staff on required AE forms and discussed by the research team during regularly scheduled meetings. Per regulations, the PI will then prepare a written report for submission to the Henry Ford Health Systems (HFHS) IRB and the appropriate NIH program officer. This report will specify all relevant information regarding whether these events were expected or unexpected, the severity of the event, a brief narrative of the event, and a determination regarding any causal connection between the event and the ongoing research study. Any such events will also be included in the annual progress report send to NIH. In the unlikely event an SAE were to occur, research staff will alert the PI immediately. Subsequent reports to the HFHS IRB and NIH will be completed within 24 hours. The expedited notice will be followed by a detailed report regarding the event.

Primary Outcomes: Delay Discounting and Consideration of Future Consequences

Descriptive statistics will be used to characterize the sample. We defined benchmark milestones *a priori* for successful change in our target mechanism (delay discounting): $\geq 50\%$ of patients participating in the intervention demonstrating decreases in delay discounting. Consideration of future consequences will be examined using descriptive statistics to evaluate distributional assumptions for parametric statistical tests. If appropriate, single-sided paired-samples *t*-tests will be used given *a priori* hypotheses regarding the direction of the effect.

Secondary Outcomes: Parenting (as measured by a behavioral task and self-report)

Descriptive statistics and distributions will be examined for all secondary outcomes. Parent-child interaction tasks were coded for positive and negative parenting behaviors using the Dyadic Parent-Child Interaction Coding System. Change in both self-reported and observed positive and negative parenting behaviors will be evaluated using single-sided paired-samples *t*-tests.

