Approximately one week after the pre-intervention assessment is completed, the participant will take part in the EFT intervention, led by a trained peer parent or the PI. The intervention session will last 75- 90 minutes in total and will be recorded for fidelity and to accurately capture each participant-generated episode. The session will begin by the PI/interventionist providing a general overview of the study and reviewing confidentiality. The participant will be asked to discuss their relationship with their child and to give examples of both positive and negative parenting from their personal experience. The interventionist will ask the participant to think about their long-term parenting goals and will discuss how to create a vivid event that will be easy to remember. Finally, several timepoints (based on important future milestones the participant identifies) will be used to create EFT events. The interventionist will create short cues from these events that will then be sent to the participant via postcard once a day for

two weeks. Cues will also be briefly discussed by the peer and participant at several points over the subsequent two weeks. The interventionist will document each check-in for tracking purposes. Peers may split the intervention into more than one meeting depending on participant need/response (related to fatigue, attention, etc.). Immediately following the intervention, parents will complete the MCQ and Parenting Joy survey again. Over the following two weeks, participants will be sent daily postcards including the cue phrase (designed to trigger recall of the future episode they identified during the intervention) and briefly meet with a peer to recall the scenes they envisioned and remind them of what they discussed during the intervention. The participant will receive \$14 at the end of two weeks for meeting regularly with the peer (between 3-7 times over the two weeks). The cumulative earned incentive amount will be paid.

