Two weeks after the intervention session, participants will complete a post-assessment battery. This assessment will include the same measures as the pre-assessment battery, with the exception of the demographics and items from the Children's Health Questionnaire. Additionally, participants will complete a brief measure of intervention satisfaction and working alliance. Peer interventionists will also be asked to rate how engaged they felt the participant was during the intervention. The post-assessment will also include a second observation session with the parent and the same child with similar tasks to the initial observation session. Participants will be given \$15 for completing the post-intervention assessment.

Following completion of the intervention, participants will also be given an opportunity to receive an additional \$15 for taking part in a 30-minute key informant interview (KII; see KII script) that gauges participants' views on their perceived acceptability and satisfaction with the intervention and study processes. These interviews will be audio-recorded; recordings will be kept on secure servers, accessible only to the study team, and deleted after 3 years. Participants will receive \$15 for completion of the KII.

After completing all study procedures, all participants will be offered a resource guide of free and low- cost resources in the Flint area.

Thus, in total, there will be four study visits/interactions: (1) the initial (baseline) assessment; (2) the intervention; (3) the post-intervention assessment; and (4) the key informant interview (which may be completed over the phone, based on participant preference).

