The interventions will be conducted by peer parents. These will be individuals who are already employed by the agency and are certified as peer recovery specialists by the State of Michigan. Agency and center staff will identify peer parents who would be appropriate to engage in this work. Peer parents will then be approached and asked if they are interested; they will be informed that working on this study is optional and that their employment is not contingent on participation. These procedures were created in conjunction with leadership from Odyssey House and peers' time will be supported by grant funding. Peers will be trained by the PI ([name]) and provided weekly and as-needed supervision, including individual review of taped session for fidelity and training purposes. All recordings of peer- participant interactions will be stored on password protected servers and will be destroyed following the three-year requirement for data storage. All peer parents (once selected) will be added to the IRB as research assistants and complete all required human subjects training. We elected to utilize peer parents given strong evidence that peers are perceived as less stigmatizing and, with training, are able to implement straight-forward interventions with fidelity.

In the event that a parent is discharged from, leaves Odyssey House after enrollment, or needs to pause study procedures for another reason, the parent will not automatically be withdrawn from the study and will be allowed to continue in the study if they wish. For those that have left Odyssey House and want to continue, we will work with the parent to determine a convenient location to complete the study.

procedures (e.g., another Odyssey House facility, their home, another residential center, etc.). In some circumstances, parents may leave Odyssey House without warning and, since we don't have their contact information, would essentially be lost to follow up unless they return to Odyssey House.

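### Meeting the 50% delay-discounting benchmark is only weak evidence of change, because it can be met by chance about half the time, and the plan does not say which follow-up MCQ counts

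*Combined protocol and SAP*

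**What the plan says.** Section 12 has a paragraph headed "Primary Outcomes: Delay Discounting and Consideration of Future Consequences". It sets a benchmark in advance for success in the target mechanism: at least 50% "of patients participating in the intervention demonstrating decreases in delay discounting". Any decrease counts. No null rate, tie rule, interval or missing-data rule is given for it.

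The same paragraph then says that consideration of future consequences will be examined descriptively, and continues: "If appropriate, single-sided paired-samples" t-tests will be used. The heading covers both outcomes, but the test sentence follows the one on future consequences. Whether it also covers delay discounting is unclear. No significance level is stated.

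Delay discounting is measured by the MCQ. Section 3 places it in the pre-assessment and repeats it twice:
- after the session: "Immediately following the intervention, parents will complete the MCQ and Parenting Joy survey again";
- at two weeks, in the post-assessment: "This assessment will include the same measures as the pre-assessment battery", with exceptions that do not include the MCQ.

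The benchmark does not say which repeat it uses. Sections 1 and 2 describe one group of up to 30 parents, all in inpatient treatment, with no control arm.

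**The concern.** A success threshold should be hard to reach when nothing has happened. This one sits at the share expected from symmetric random variation when no score is unchanged. In that case a parent group with no true change would pass about as often as a coin lands heads.

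The benchmark is the only numerical success criterion in the supplied text for Aim 2a (preliminary efficacy on delay discounting), and Section 3 says the findings will be used to adapt the intervention for a larger randomised trial. A bare pass, reported under the plan's own label of success, could be read as engagement of the mechanism when the data are equally compatible with no change.

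The unnamed follow-up reading adds a second gap. A reading straight after the session and one after two weeks of cues and peer check-ins answer different questions.

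**Working it through.** The plan gives no power or error figure for the benchmark, so there is none to reproduce.

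**Inputs.** From the documents: n up to 30; pass if the number decreasing, X, is at least n/2. Assumed: with no effect and no drift, the chance that a parent decreases is p = (1 − tie share)/2. The documents give neither a tie rate nor a drift, so ranges are shown.

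**1. No effect, no ties (p = 0.5).** P(pass) = P(X ≥ ⌈n/2⌉), X ~ Bin(n, 0.5). At n=30, P(X=15) = 0.1445, so by symmetry P(X ≥ 15) = 0.5 + 0.1445/2 = 0.572.

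| n | needed | P(pass) |
|---|---|---|
| 10 | 5 | 0.623 |
| 20 | 10 | 0.588 |
| 25 | 13 | 0.500 |
| 30 | 15 | 0.572 |

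Odd n gives exactly 0.500.

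**2. Ties, n=30.** Unchanged scores count against the benchmark.

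| tie share (assumed) | p | P(X ≥ 15) |
|---|---|---|
| 0% | 0.50 | 0.572 |
| 10% | 0.45 | 0.355 |
| 20% | 0.40 | 0.175 |
| 30% | 0.35 | 0.065 |

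**3. Drift, n=30.** A background shift of 0.2 SD of the change score (assumed, normal changes) gives p = Φ(0.2) = 0.579 and P(X ≥ 15) = 0.856.

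**4. What a pass or a miss tells us.** With a true share of 75%, P(X ≥ 15 | n=30) = 0.999, so a miss is strong evidence against an effect of that size. A pass is weak evidence for it: the likelihood ratio against no effect is 0.999/0.572 ≈ 1.7 with no ties. With 10% ties, and 75% of untied scores falling, it is 0.985/0.355 ≈ 2.8. An observed 15/30 has an exact (Clopper-Pearson) 95% CI of 31% to 69%.

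**5. Missing follow-up, no effect, no ties.** If 3 of 30 have no follow-up score (assumed), the pass rate is P(Bin(27, 0.5) ≥ 14) = 0.500 among completers, or P(Bin(27, 0.5) ≥ 15) = 0.351 if all 30 form the denominator. If 6 are missing, the two figures are P(Bin(24, 0.5) ≥ 12) = 0.581 and P(Bin(24, 0.5) ≥ 15) = 0.154. The rule for missing scores therefore matters.

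**6. The paired t-test instead** (one-sided 5% assumed, normal changes, noncentral t with noncentrality d√n). A true share of 75% corresponds to d = Φ⁻¹(0.75) = 0.674, and 65% to d = 0.385. At n=30 the power is 0.975 and 0.66; at n=20 it is 0.90 and 0.51. A matching 90% CI for the mean change has half-width 1.699/√30 = 0.31 SD at n=30. A 95% CI would not match: at d = 0.385 and n=30 it lies wholly on the decrease side with probability 0.53, while the test passes with probability 0.66.

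**The case against.** The strongest reply is that this is a pilot case series, where a descriptive milestone is legitimate. Section 1 calls the efficacy aim preliminary, and no section makes the larger trial conditional on the benchmark. That stands, and it is why 50% can remain as a minimum milestone. It does not rescue the label of success for a bare pass.

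Ties also weaken the headline: at 30% ties a chance pass is rare (0.07). But drift works the other way, and neither quantity is given, so the false-pass rate is uncontrolled.

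Some stronger readings are tempting but not supported:
- A reader might infer that a pass is no evidence at all. The likelihood ratios above exceed 1, and a result well above half, such as 25/30, also meets the benchmark and would say more.
- A reader might infer that a pass at either follow-up reading counts, which would raise the chance-pass rate further. No section allows this. The two-week post-assessment is the natural pair to the pre-assessment; the plan simply does not say so for the benchmark.
- A reader might infer that participants reported to authorities are left uncounted by oversight. Section 4 does state the rule: "but their data will not be used and a replacement participant will be recruited". The open question concerns parents who leave without warning and "would essentially be lost to follow up unless they return to Odyssey House".
- A reader might infer from "Parent-child interaction tasks were coded for positive and negative parenting behaviors" that delay-discounting data have already been examined. That sentence concerns the observation tasks, a secondary outcome, and Section 12 places analysis after all data are collected.

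**Conclusion.** The concern holds in a limited form. With no effect, no ties and no drift, the benchmark is met with probability 0.57 at n=30. Across the assumed tie rates and drift at n=30, the chance-pass rate runs from 0.07 to 0.86. Meeting the benchmark is only weak evidence of change, while missing it is informative. The result rests on an equal chance of rise and fall among untied scores, independent participants, and assumed tie and drift values.

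The missing specification of the follow-up MCQ is a matter of text and needs no assumption. Both points should be fixed; neither undermines the feasibility aims.

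**What to change.** 1. Keep 50% as a minimum milestone, and do not describe meeting it alone as success in changing the mechanism.
2. State that the one-sided paired t-test in Section 12 also covers delay discounting, and name its level. Base any statement of change on the mean change in the MCQ score, with an interval matched to that test (for example one-sided 5% with a 90% CI). Fix the score's scale in advance (for example log-transformed), and name a fallback, such as the signed-rank test, if the changes are clearly non-normal. Report alongside it the share with a decrease, its exact 95% CI and the number unchanged.
3. Before the data are examined, name one follow-up MCQ reading for the benchmark (the two-week post-assessment is the natural choice) and report the other as secondary. Take the share among participants with both readings, and add a sensitivity result that counts missing scores as not decreased.
4. State that in this single-arm design neither the benchmark nor the t-test separates the intervention from drift due to concurrent inpatient treatment or retesting. A 0.2 SD drift would pass the t-test with probability 0.28 at n=30, against 0.86 for the benchmark. That gap reflects a higher bar; the bias in the mean change is the same.

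**Cost.** No new data collection. Success is harder to declare: power at n=30 is 0.975 for a true share of 75% but only 0.66 for 65%, and both fall with fewer completers (0.90 and 0.51 at n=20).
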